### 6.4 STUDY INTERVENTION/EXPERIMENTAL MANIPULATION ADHERENCE

Participation in all four sessions (MRI and three stimulation sessions) is mandatory for participants to remain active participants in the study. Participation will be tracked across sessions by a single ID number associated with all data collected across the three sessions. All study components will be completed within one of the four sessions, so there is no issue of adherence beyond those four sessions.

### 6.5 CONCOMITANT THERAPY

N/A

#### 6.5.1 RESCUE THERAPY

N/A

### 7 STUDY INTERVENTION/EXPERIMENTAL MANIPULATION DISCONTINUATION AND PARTICIPANT DISCONTINUATION/WITHDRAWAL

#### 7.1 DISCONTINUATION OF STUDY INTERVENTION/EXPERIMENTAL MANIPULATION

Reasons for discontinuation of a stimulation (TMS) session include discomfort or expressed desired to discontinue a TMS session. Some individuals receiving TMS, for example, have reported headaches associated with stimulation and may request discontinuation.

When a subject discontinues from a TMS session, and a clinically significant finding is identified after enrollment, the investigator will determine if any change in participant management is needed. Any new clinically relevant finding will be reported as an adverse event (AE).

The data to be collected at the time of study intervention discontinuation will include the following:

- The reason(s) for discontinuing the participant from the intervention

#### 7.2 PARTICIPANT DISCONTINUATION/WITHDRAWAL FROM THE STUDY

Participants are free to withdraw from participation in the study at any time upon request.

An investigator may discontinue a participant from the study for the following reasons:

- Identification of brain abnormalities during the MRI scan
- Non-compliance with regards to cognitive task instructions
- Lost-to-follow up; unable to contact subject (see **Section 7.3, Lost to Follow-Up**)
- Any event or medical condition or situation occurs such that continued collection of follow-up study data would not be in the best interest of the participant or might require an additional treatment that would confound the interpretation of the study; With TMS an unlikely but possible medical condition would be onset of a seizure
- The participant meets an exclusion criterion (either newly developed or not previously recognized) that precludes further study participation

The reason for participant discontinuation or withdrawal from the study will be recorded on the Case Report Form (CRF). Subjects who sign the informed consent form and are randomized but do not receive the study intervention may be replaced. Subjects who sign the informed consent form, and are randomized and receive the study intervention, and subsequently withdraw, or are discontinued from the study, will be replaced.

### 7.3 LOST TO FOLLOW-UP

A participant will be considered lost to follow-up if he or she fails to appear for the MRI session, or appear or return for two scheduled stimulation sessions and study staff are unable to contact the participant after at least 3 attempts.

The following actions must be taken if a participant fails to return for a required study visit:

- The site will attempt to contact the participant, reschedule the missed visit within one week, counsel the participant on the importance of maintaining the assigned visit schedule and ascertain if the participant wishes to and/or should continue in the study
- Before a participant is deemed lost to follow-up, the investigator or designee will make every effort to regain contact with the participant (3 emails). These contact attempts will be documented in the participant's medical record or study file.
- Should the participant continue to be unreachable, he or she will be considered to have withdrawn from the study with a primary reason of lost to follow-up

## 8 STUDY ASSESSMENTS AND PROCEDURES

### 8.1 ENDPOINT AND OTHER NON-SAFETY ASSESSMENTS

During the screening process, participants will be informed about basic inclusion / exclusion criteria after they first contact us, by email. We will then ask participants questions, by phone, on the MRI and TMS screening forms in detail and indicate whether they meet criteria or not. Although we will not yet ask participants to fill out these forms (i.e. no data will be recorded at this stage), we will ask them to confirm that they meet all criteria on the forms, prior to scheduling their first visit. Within two weeks of this confirmation, we will invite participants for their first session visit.

At the first visit, participants will complete the informed consent process and then be asked to fill out the screening forms, after giving consent. These data will include information about psychiatric or psychological history, presence or absence of metal in the body, history of physical trauma to the brain, current alcohol or drug abuse, current use of psychiatric medications, and use of other medications which may lower the seizure threshold. We will also collect basic demographic and handedness information.

Following the informed consent process the following data will be collected during the study.

- **Performance-based assessments:** Oculmotor task performance, decision-making task performance
- **Questionnaires:** The Need for Cognition Scale
- **Imaging assessments:** Using a 64-channel EEG system, we will record brain waves at the scalp throughout all procedures during the stimulation session. In the MRI scanner we will collect several types of scans. For the purposes of TMS neuro-navigation, we will collect T1 MPRAGE sequences, structural localizer scans, functional localizer scans, and a field map scan. We will also collect 10-12 minutes of resting state fMRI data. These data will be collected on a 3T MRI.

## 8.2 SAFETY ASSESSMENTS

N/A

## 8.3 ADVERSE EVENTS AND SERIOUS ADVERSE EVENTS

### 8.3.1 DEFINITION OF ADVERSE EVENTS

This protocol uses the definition of adverse event from 21 CFR 312.32 (a): any untoward medical occurrence associated with the use of an intervention in humans, ***whether or not considered intervention-related.***

### 8.3.2 DEFINITION OF SERIOUS ADVERSE EVENTS

Any adverse event that (i) results in death; (ii) is life-threatening (places the subject at immediate risk of death from the event as it occurred); (iii) results in inpatient hospitalization or prolongation of existing hospitalization; (iv) results in persistent or significant disability/incapacity; (v) results in congenital anomaly/birth defect; or (vi) based upon appropriate medical judgement, may jeopardize the subject's

health and may require medical or surgical intervention to prevent one of the other outcomes listed in this definition.

### 8.3.3 CLASSIFICATION OF AN ADVERSE EVENT

#### 8.3.3.1 SEVERITY OF EVENT

For adverse events (AEs) not included in the protocol defined grading system, the following guidelines will be used to describe severity.

- **Mild** – Events require minimal or no treatment and do not interfere with the participant's daily activities.
- **Moderate** – Events result in a low level of inconvenience or concern with the therapeutic measures. Moderate events may cause some interference with functioning.
- **Severe** – Events interrupt a participant's usual daily activity and may require systemic drug therapy or other treatment. Severe events are usually potentially life-threatening or incapacitating. Of note, the term "severe" does not necessarily equate to "serious".

#### 8.3.3.2 RELATIONSHIP TO STUDY INTERVENTION/EXPERIMENTAL MANIPULATION

All adverse events (AEs) will have their relationship to study procedures, including the intervention, assessed by an appropriately-trained clinician based on temporal relationship and his/her clinical judgment. The degree of certainty about causality will be graded using the categories below.

- **Related** – The AE is known to occur with the study procedures, there is a reasonable possibility that the study procedures caused the AE, or there is a temporal relationship between the study procedures and the event. Reasonable possibility means that there is evidence to suggest a causal relationship between the study procedures and the AE.
- **Not Related** – There is not a reasonable possibility that the study procedures caused the event, there is no temporal relationship between the study procedures and event onset, or an alternate etiology has been established.

#### 8.3.3.3 EXPECTEDNESS

A clinician with appropriate expertise in transcranial magnetic stimulation will be responsible for determining whether an adverse event (AE) is expected or unexpected. An AE will be considered

unexpected if the nature, severity, or frequency of the event is not consistent with the risk information previously described for the study procedures.

---

#### 8.3.4 TIME PERIOD AND FREQUENCY FOR EVENT ASSESSMENT AND FOLLOW-UP

The occurrence of an adverse event (AE) or serious adverse event (SAE) may come to the attention of study personnel during study visits and interviews of a study participant presenting for medical care, or upon review by a study monitor.

All AEs, not otherwise precluded per the protocol, will be captured on the appropriate case report form (CRF). Information to be collected includes event description, time of onset, clinician's assessment of severity, relationship to study procedures (assessed only by those with the training and authority to make a diagnosis), and time of resolution/stabilization of the event. All AEs occurring while on study will be documented appropriately regardless of relationship. All AEs will be followed to adequate resolution.

Any medical or psychiatric condition that is present at the time that the participant is screened will be considered as baseline and not reported as an AE. However, if the study participant's condition deteriorates at any time during the study, it will be recorded as an AE.

Changes in the severity of an AE will be documented to allow an assessment of the duration of the event at each level of severity to be performed. Documentation of onset and duration of each episode will be maintained for AEs characterized as intermittent.

The Principal Investigator will record events with start dates occurring any time after informed consent is obtained until 7 (for non-serious AEs) or 30 days (for SAEs) after the last day of study participation. At each study visit, the investigator will inquire about the occurrence of AE/SAEs since the last visit. Events will be followed for outcome information until resolution or stabilization.

---

#### 8.3.5 ADVERSE EVENT REPORTING

##### **Reportable Events**

Principal Investigators must report to Rutger's HRPP the occurrence of any of the events described below, collectively referred to as Reportable Events:

- Any Adverse Event (AE) that (1) is a UAE and (2) is related or possibly related to participation in the research.
- Any UP.
- Any breach of Privacy or Confidentiality, including lost or stolen confidential information of a research participant.
- Any medical, procedural, or laboratory error potentially increasing risk to participants (e.g., errors in drug administration or dosing, surgical or other procedures, testing of samples, or test results).
- Any interim analysis, safety monitoring report, publication in a peer-reviewed journal, or other finding indicating that there are new or increased risks to subjects or others, or that subjects are less likely to receive any direct benefits from the research study than as initially presented to the IRB or HRPP.
- Any complaint by or on behalf of a subject indicating that the rights, welfare, or safety of the subject have been adversely affected.
- Any change in the Food and Drug Administration (FDA) labeling; any change in the status of an Investigational New Drug Application (IND) or Investigational Device Exemption (IDE); any withdrawal from market; any manufacturer alert from the sponsor of the research study; or any recall of an FDA-approved drug, device, or biologic under investigation in the research study.
- Any event that requires prompt reporting to the sponsor of the research study, when applicable.
- A Suspension or Termination of a research study or of a study's enrollment, including by the FDA or the sponsor of the research study, based on information indicating that the research study places subjects at an increased risk of harm than was previously known or recognized.
- Any other event that is unanticipated (irrespective of any "relatedness" to the research) and indicates that the research study places subjects or others (e.g., other investigators, research assistants, students, the public, family members or partners of subjects) at an increased risk of harm or otherwise adversely affects the rights, welfare, or safety of subjects or others.

### **Reporting Timeframes**

Principal Investigators must report Reportable Events to the HRPP in accordance with the following timeframes:

- Reportable Events that are either life-threatening or have resulted in death must be reported to the HRPP via telephone, or email if phone is not possible, within one business day from the date the PI is notified of or discovers the Reportable Event. The PI must ensure that Research Personnel are trained to report any Reportable Event to the PI promptly upon discovery, and no later than 24 hours following its discovery or occurrence. A Reportable Events Form must be submitted to

the HRPP within 48 hours of the PI's initial verbal or email notification to the HRPP of the Reportable Event.

- Reportable Events that are not life-threatening and have not resulted in death must be reported to the HRPP in writing as soon as possible, and no later than 7 business days from the date the PI is notified of or discovers the Reportable Event.
- Minor Protocol Deviations must be reported to the HRPP in writing at the time of continuing review when continuing review is applicable to the study protocol, and must be reported during any quality assurance/quality improvement assessment by the HRPP. If continuing review is not applicable to the study protocol, the PI must maintain Minor Protocol Deviations as part of the study record and make the study record available upon request to the IRB, HRPP, and/or any federal sponsor or regulatory agency, as applicable.

### **Reporting Reportable Events**

In accordance with the timeframes outlined above, PIs must submit to the HRPP a Reportable Events Form and include the following information:

- Identifying information for the research study, including the study title, the PI's name, and the IRB protocol number;
- A detailed description of the Reportable Event, including relevant dates and times;
- A detailed description of any corrective action or change to the protocol, planned or already taken, to ensure that the Reportable Event is corrected and will not occur again;
- An assessment of whether any research participants or others were placed at risk as a result of the Reportable Event, or suffered any physical, social, or psychological harm and any plan to address these consequences; and
- Any other information deemed relevant by the PI

---

#### **8.3.6 SERIOUS ADVERSE EVENT REPORTING**

The PI will be responsible for conducting an evaluation of a serious adverse event and shall report the results of such evaluation to the NIH and the reviewing Institutional Review Board (IRB) as soon as possible, but in no event later than 7 working days after the event.

---

#### **8.3.7 REPORTING EVENTS TO PARTICIPANTS**

Incidental findings related to the structural MRI scans are possible. MRIs are collected at the Rutgers' Center for Advanced Human Brain Imaging Research and any possible incidental findings will be flagged for review by an MD at Rutgers' Robert Wood Johnson Medical School who will convey any reportable anomalies to participants directly if any are identified.

#### 8.3.8 EVENTS OF SPECIAL INTEREST

N/A

#### 8.3.9 REPORTING OF PREGNANCY

If participants indicate during screening that there is a chance they may be pregnant, we supply and ask participants to take a pregnancy test to ensure that they are not pregnant. If they are pregnant they will be withdrawn from the study and all procedures (MRI, TMS) for safety reasons.

### 8.4 UNANTICIPATED PROBLEMS

#### 8.4.1 DEFINITION OF UNANTICIPATED PROBLEMS

This protocol uses the definition of Unanticipated Problems as defined by the Office for Human Research Protections (OHRP). OHRP considers unanticipated problems involving risks to participants or others to include, in general, any incident, experience, or outcome that meets all of the following criteria:

- Unexpected in terms of nature, severity, or frequency given (a) the research procedures that are described in the protocol-related documents, such as the Institutional Review Board (IRB)-approved research protocol and informed consent document; and (b) the characteristics of the participant population being studied;
- Related or possibly related to participation in the research ("possibly related" means there is a reasonable possibility that the incident, experience, or outcome may have been caused by the procedures involved in the research); and
- Suggests that the research places participants or others at a greater risk of harm (including physical, psychological, economic, or social harm) than was previously known or recognized.

UPs may warrant corrective actions. Examples of corrective actions or changes that might need to be considered in response to an UP include:

- Modification of inclusion or exclusion criteria to mitigate the newly identified risks
- Implementation of additional safety monitoring procedures
- Suspension of consenting/enrollment of new participants or halting of study procedures for consented/enrolled participants
- Modification of informed consent documents to include a description of newly recognized risks
- Provision of additional information about newly recognized risks to previously consented/enrolled participants.

---

#### 8.4.2 UNANTICIPATED PROBLEMS REPORTING

The principal investigator (PI) will report unanticipated problems (UPs) to the reviewing Institutional Review Board (IRB). The UP report will include the following information:

- Protocol identifying information: protocol title and number, PI's name, and the IRB project number
- A detailed description of the event, incident, experience, or outcome
- An explanation of the basis for determining that the event, incident, experience, or outcome represents an UP
- A description of any changes to the protocol or other corrective actions that have been taken or are proposed in response to the UP

To satisfy the requirement for prompt reporting, UPs will be reported using the following timeline:

- UPs that are serious adverse events (SAEs) will be reported to the IRB and to the DCC/study sponsor/funding agency within 1 business day of the investigator becoming aware of the event
- Any other UP will be reported to the IRB and to the DCC/study sponsor/funding agency within 7 business days of the investigator becoming aware of the problem
- All UPs should be reported to appropriate institutional officials (as required by an institution's written reporting procedures), the supporting agency head (or designee), and the Office for Human Research Protections (OHRP) within one month of the IRB's receipt of the report of the problem from the investigator

---

#### 8.4.3 REPORTING UNANTICIPATED PROBLEMS TO PARTICIPANTS

For UPs that impact on all participants, all participants will be notified within two weeks, in writing, of the UP and corrective actions which have been taken.

## 9 STATISTICAL CONSIDERATIONS

There will not be a formal Statistical Analysis Plan (SAP). Also, no statistical plan will be posted publicly or registered before the study begins.

### 9.1 STATISTICAL HYPOTHESES

- Primary Endpoint(s):

We predict that, relative to pre-stimulation rest, continuous theta burst stimulation (cTBS) will result in a reduction of the local balance of cortical excitation to inhibition as reflected in the functional E/I balance in proximity to stimulated targets. Conversely, we predict that intermittent theta burst stimulation (iTBS) will result in an increase of the local balance of cortical excitation to inhibition as reflected in the functional E/I balance in proximity to stimulated targets. We also predict these changes to exceed any effects of sham stimulation, and thus another set of endpoints will compare the functional E/I balance after sham versus either active stimulation protocol.

We also predict that, relative to pre-stimulation rest, cTBS and iTBS protocols that will either reduce or strengthen markers of critical dynamics (including, e.g., long-range temporal correlations) in proximity to stimulation targets. The direction of the effect will depend on how the brain operates at baseline. For example a brain that operates in a more sub-critical (lower E/I balance) regime will show an increase in long-range temporal correlations following iTBS (because it should raise the functional E/I balance).

We also predict that, relative to sham stimulation, cTBS and iTBS will alter oculomotor task performance. Specifically, because criticality makes brains more flexible and susceptible, protocols which make brains operate closer to criticality will cause performance to become more variable and worse on the memory-guided saccade task which depends on stability of short-term memory representations. Also, because criticality increases information transfer capacity between brain regions, protocols which make brains operate closer to criticality will cause performance to become better on the anti-saccade task which depends on robust top-down communication of control signals to override bottom-up reflexive saccades to the target.

We also predict that, relative to sham stimulation, cTBS and iTBS will alter subjective effort. We hypothesize that subjective effort reflects divergence from criticality associated with performing difficult tasks. Indeed, typically, brains become more sub-critical, on average, when performing demanding tasks. To measure subjective effort, we will examine cognitive effort discounting – a measure of the amount by which participants discount the offer to perform a more demanding version of tasks (in this case with frequent task switching between anti- and pro-saccades) versus a less demanding version of the task (in this case with minimal task switching between anti- and pro-saccades) for money. The amount of money people forgo to avoid the harder task quantifies the subjective effort cost they experience. We predict

that people whose brains diverge more from criticality during task performance will show steeper effort discounting, and that cTBS or iTBS protocols that minimize divergence from criticality during the task will show shallower effort discounting.

We also hypothesize that subjective effort reflects divergence from a critical state and that criticality depends on the E/I balance. As such, we predict that there will be individual difference correlations in the degree to which TMS perturbs E/I balance, alters measures of criticality including long-range temporal correlations, and ultimately amplifies subjective effort.

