Test whether theta-burst stimulation to the frontal eye fields (FEF) alters short term memory relative to sham stimulation.	Increases or decreases in accuracy and trial-to-trial variability in the memory-guided saccade task.	Criticality affords greater dynamic susceptibility to afferent inputs. As such, brains operating closer to criticality will more dynamic instability, undermining performance on tasks dependent on short term memory stability. Theta-burst manipulations which push brains closer to criticality will thus produce greater trial-to-trial variability in accuracy and reaction times on tasks	A decrease in the E/I balance in the FEF following cTBS or an increase in E/I balance following iTBS will make the FEF operate closer to criticality for some people and farther away for others. Operating closer to criticality as a consequence of TMS will thereby cause instability in the short-term

OBJECTIVES	ENDPOINTS	JUSTIFICATION FOR ENDPOINTS	PUTATIVE MECHANISMS OF ACTION
		including memory-guided saccades.	memory representations needed for memory-guided saccades.
Test whether cTBS increases and iTBS decreases subjective cognitive effort associated with task switching between anti- and pro-saccades.	Task switch costs and effort discounting of rewards contingent on the expenditure of cognitive effort following active versus sham FEF stimulation.	Task switching is effortful and subjectively costly, producing effort avoidance. Brains operating closer to criticality have more dynamical flexibility and so should reduce switch costs and subjective effort.	A decrease in the E/I balance in the FEF following cTBS or an increase in E/I balance following iTBS will make the FEF operate closer to criticality for some people and farther away for others. Operating closer to criticality as a consequence of TMS will thereby cause result more dynamical flexibility reducing the energy required to shift neural dynamics between tasks, and thereby produce lower effort costs.
Secondary			
Tertiary/Exploratory			

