### 6.3 MEASURES TO MINIMIZE BIAS: RANDOMIZATION AND BLINDING

All participants will complete both one sham and two active stimulation sessions, but the order of these sessions will be pseudo-randomized. Specifically, participants will be assigned participant ID numbers based on their order of recruitment, but the participant ID numbers will be pseudo-randomized with respect to double-blind-coded active versus sham stimulation. Pseudo-randomization of double-blind codes will be generated by a script and saved in a digital file. The de-blinding key to this digital file will be saved by a collaborator not directly involved in conduct of the study and will not be accessed by study personnel until the end of data collection.

The specific session that a participant is in (active versus sham stimulation) will be unknown to the experimenter since the stimulator is only set to function in active or sham stimulation model based on the double-blind codes. To maintain blinding, the experimental condition will not be explained to the participant until after the conclusion of data collection, at the participants' request.

While it may be possible for some participants to infer the distinction between active and sham stimulation, we will not discuss conditions with participants nor will we discuss with participants our predictions about how active versus sham stimulation should differentially impact oculomotor control.

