## 9.2 SAMPLE SIZE DETERMINATION

While studies on the effects of continuous theta-burst stimulation (cTBS) and intermittent theta burst stimulation (iTBS) on critical dynamics have never been conducted, power calculations are based on prior work showing that cTBS and iTBS can alter cortical excitability. Effect sizes were taken from a meta-analysis of the effects of cTBS and iTBS on motor cortex excitability, as measured by motor evoked potential via electrodes attached at the contralateral hand (Chung et al. 2016). Two trains of cTBS were found to reliably decrease (Hedge's  $g$  20-30 min after stimulation:  $g = -1.14$ ), and iTBS reliably increase ( $g = .84$ ), motor evoked potentials. Using  $g^*Power$  (Faul et al., 2007), we estimate that if the true effect size remains the same, we will have  $> 95\%$  power to detect a cTBS effect in a sample of 60 participants at  $p < 0.05$ . As such, our target recruitment is set at 60 participants (but will recruit additional participants to reach 60 complete participant-session sets, as needed, due to drop-out). At a later timepoint (50-60 minutes after stimulation) two trains of cTBS have a lasting effect of ( $g = -1.18$ ) while the effects of iTBS are diminished ( $g = -.21$ ). This means that we should still be able to detect a lasting effect of cTBS with  $> 95\%$  power at this later timepoint, while power drops to 36% for iTBS.

While effect sizes can vary in rTMS owing to considerable inter-individual differences in response to stimulation, we are taking additional measures to reduce reliability including participant-specific brain images and neuronavigation, and also the use of two, rather than one train of rTMS.

While this estimate is based on motor cortex excitability alone, this outcome is arguably the most direct measure of the effects of rTMS on cortical excitability. Some caution is warranted because it is unclear whether the effects of cortical excitability on motor cortex are predictive of rTMS effects outside of motor cortex.

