## 9.4 STATISTICAL ANALYSES

### 9.4.1 GENERAL APPROACH

There are no categorical outcomes. Key measures are all continuous outcomes, and are described in detail in the next section. They will be analyzed according to pre- versus post-stimulation means and also in sham versus active stimulation. We will also report standard errors for each outcome. Key outcomes have multiple associated measures. Multiple measures will be used to assess reliability by parallel forms.

We will use standard frequentist cut-offs of  $p < 0.05$  for all statistical tests, correcting for multiple comparisons. Key t-tests will include pre-post and sham-versus-active distinctions in E/I balance measures, oculomotor control task performance measures, and measures of criticality.

Covariates of no interest to be included are sex and age which we will incorporate via multiple regression to ask whether rTMS alters key outcomes (described in the next session).

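### cTBS and iTBS are predicted to move functional E/I in opposite directions, yet no planned test compares them and the primary model has no iTBS term

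*Protocol*

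**What the plan says.** - **Predictions.** Section 9.1 predicts that cTBS lowers functional E/I near the target and that iTBS raises it, with no condition attached. Section 3 also gives opposite signs for anti-saccade accuracy and for effort: "Test whether cTBS increases and iTBS decreases subjective cognitive effort associated with task switching between anti- and pro-saccades".
- **Planned comparisons.** In 9.1, besides the comparison with pre-stimulation rest, "another set of endpoints will compare the functional E/I balance after sham versus either active stimulation protocol". In 9.4.1, "Key t-tests will include pre-post and sham-versus-active distinctions in E/I balance measures", with the same for task performance and criticality measures. Section 4.3 justifies the three sessions by the active-versus-sham comparison.
- **Primary model.** Section 9.4.2 regresses each outcome on cTBS (target versus sham) with sex and age. iTBS does not appear.
- **Data available.** Sections 4.4 and 6.3 have each participant complete one sham and two active sessions. The sample is 60 complete sets; the sponsor "will recruit additional participants to reach 60 complete participant-session sets, as needed, due to drop-out".
- **Blinding.** Section 6.3 accepts a limit: "While it may be possible for some participants to infer the distinction between active and sham stimulation".
- **Deferral.** The opening of section 9 states that there will be no formal SAP, so this contrast is not left to another document.

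**The concern.** A prediction that two interventions act in opposite directions is a statement about the difference between them. Two separate tests against a common sham do not estimate that difference. If one is significant and the other is not, nothing follows about whether cTBS and iTBS differ, and that pattern is plausible here: section 9.2 gives power above 95% for cTBS at 50-60 minutes, "while power drops to 36% for iTBS".

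The sham contrasts are also the ones that guessing can bias. Effort ratings, motivation scales and discounting choices are open to expectancy. Any shift shared by both active sessions enters each active-versus-sham difference in full and cancels in iTBS minus cTBS.

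As written, the primary model does not estimate an iTBS effect at all, although half of the directional E/I prediction concerns iTBS.

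**Working it through.** **Inputs.** From 9.2: 60 participants, all paired; cTBS g = -1.14 and iTBS g = +0.84 at 20-30 minutes; -1.18 and -0.21 (as printed) at 50-60 minutes. From 9.4.1: "We will use standard frequentist cut-offs of" p < 0.05; sidedness is not stated. Assumptions not in the protocol: g is used as the standardised paired difference, and the three pairwise differences have equal SDs.

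**Formula.** Paired t-test, df = 59, noncentrality |g| × √60, two-sided 0.05 without multiplicity adjustment, power from the noncentral t.

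**Reproducing the plan.** For |g| = 0.21, noncentrality is 0.21 × 7.746 = 1.627 and power is 36.0%, matching the stated 36%. (One-sided gives 48.5%; two independent groups of 60 give 20.7%.) For 1.14 and 1.18 power is above 99.9%, consistent with the stated >95% "power to detect a cTBS effect in a sample of 60 participants at" p < 0.05.

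**Direct contrast, g(iTBS) − g(cTBS).**
- 20-30 minutes: 0.84 − (−1.14) = 1.98, which is 1.98/1.14 = 1.74 times the cTBS-sham effect and 1.98/0.84 = 2.36 times the iTBS-sham effect.
- 50-60 minutes, as printed: −0.21 − (−1.18) = 0.97, smaller than cTBS-sham at 1.18. If the sign was meant as +0.21, it is 1.39.

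**Power at 20-30 minutes.** Section 9.2 itself cautions that motor-cortex effects may not carry over to other regions. The scaling below is an assumption, shown as a range.

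| Share of stated effect | cTBS-sham | iTBS-sham | iTBS-cTBS |
|---|---|---|---|
| 100% | >99.9% | >99.9% | >99.9% |
| 50% | 99.1% | 89.3% | >99.9% |
| 25% | 58.4% | 36.0% | 96.5% |
| 15% | 25.6% | 16.0% | 61.9% |
| 10% | 14.0% | 9.8% | 32.6% |

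At 25% of the 50-60 minute values, the direct contrast has 45.5% power against 61.3% for cTBS-sham; with +0.21 it would have 75.4%.

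**Sensitivity to the SD assumption.** If g is instead a pre-post effect and the change scores in two sessions correlate at r, each contrast is divided by √(2(1 − r)). At 25% of the 20-30 minute effects, power (direct, cTBS-sham, iTBS-sham) is 76.0%, 33.6%, 20.5% at r = 0 and 99.8%, 80.0%, 54.2% at r = 0.7. The ordering does not change.

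**Guessing.** Suppose no true effect and a shift common to both active sessions, in SDs of the paired difference (assumed). Each sham contrast is then falsely significant in 11.9% of trials at 0.1, 33.2% at 0.2 and 62.8% at 0.3. The direct contrast stays at 5%.

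**The case against.** **The planned tests answer the stated questions.** The synopsis and sections 3, 4.3 and 9.1 frame effects relative to sham or to pre-stimulation rest. If cTBS is significantly below sham and iTBS significantly above it, the ordering follows. This stands: the protocol nowhere claims a cTBS-iTBS difference from unequal p-values. But it has no valid test for the likelier case in which only one sham contrast is significant.

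**The direction is not fixed for every outcome.** Section 3 (the mechanism given for effort) and sections 6.1.1 and 9.1 say that stimulation may bring some participants nearer criticality and take others further from it, and make the change in long-range temporal correlations depend on baseline. Section 9.1 ties task performance and discounting to distance from criticality rather than to the protocol delivered. A mean iTBS-cTBS difference could then be near zero while the hypothesis is true. This stands, and limits the key test to functional E/I.

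**A reader might infer that the direct contrast is always the strongest test.** The documents do not support that. At the stated 20-30 minute effects there is no gain in power, and at the printed 50-60 minute effects it is weaker than cTBS-sham.

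**A reader might also infer that it is free of blinding bias.** It is not. Sections 4.1 and 6.1.2 describe one pattern as continuous for 40 seconds and the other as 2-second trains with pauses. Sections 6.1.1 and 6.3 claim masking only for active versus sham. Recognition of the pattern can still bias the contrast.

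**Conclusion.** The concern holds in limited form. The plan predicts opposite effects on functional E/I, collects both active conditions in each participant, and specifies no test of their difference; its primary model omits iTBS. The loss is mainly in inference and in robustness to active-versus-sham guessing. Loss of power is conditional: none at the 20-30 minute planning effects, and 96.5% against 58.4% and 36.0% if effects are a quarter of those. These figures rest on g as a paired standardised effect, equal SDs of the pairwise differences and no multiplicity adjustment. The scaling factors and guessing shifts are illustrations, not protocol values.

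It would go too far to make the direct contrast a condition for any conclusion on effort. The protocol gives effort a signed prediction in one place and a baseline-dependent one in others, and such a gate would enforce one side of an unresolved conflict.

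**What to change.** 1. In 9.4.1 and 9.4.2, replace the cTBS-only regressor with a within-participant model that has a three-level condition (sham, cTBS, iTBS).
2. Prespecify iTBS minus cTBS as a key test for functional E/I, and keep both sham contrasts to show which protocol drives any difference.
3. Report the same contrast as supportive for anti-saccade accuracy and effort, without making it a gate.
4. Reconcile the signed predictions in section 3 with the baseline-dependent ones in sections 3, 6.1.1 and 9.1.
5. Check the sign of the 50-60 minute iTBS effect in 9.2, since it decides whether the direct contrast is larger or smaller than cTBS-sham at that time.
6. State that the direct contrast removes bias common to active stimulation but not bias from recognising the pattern.

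Cost: no new data, visits or participants. The multiplicity family grows by one test per outcome given the contrast. That is more than one test in all, because 9.4.2 lists four types of effort measure, one with four ratings; naming one effort measure for the contrast would limit this.
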